2. We hypothesize that the fold increase in Varicella Zoster Virus (VZV)-specific immunity in subjects with solid organ tumors that were given ZOSTAVAX at least 14 days prior to initiation of chemotherapy will be higher than the control group that is not vaccinated.
3. We hypothesize that immediately before the second cycle of chemotherapy VZV-specific immunity will be higher in those subjects that received ZOSTAVAX prior to chemotherapy than those that were not vaccinated.
4. We hypothesize that at 3-18 months post-chemotherapy VZV-specific immunity will be higher in those subjects that received ZOSTAVAX prior to chemotherapy than those that were not vaccinated.
5. We hypothesize that ZOSTAVAX is safe if given to subjects with solid organs tumors at least 14 days prior to initiation of chemotherapy or surgery followed by chemotherapy.

10. Describe the means of analyzing the data and evaluating the results.

- *State the anticipated methods to be used for analysis and interpretation of the data.*
- *The methods must compliment the design of the study and the nature of the data which is being collected.*

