	Research Staff	LSCDVAMC Clinical or Support Staff	Standard of Care*	For Research Purposes Only**

PROCEDURE	PERFORMED BY:		PROCEDURE IS:	
	Research Staff	LSCDVAMC Clinical or Support Staff	Standard of Care*	For Research Purposes Only**
Audiotaping / Videotaping Attach VA Form 10-3203 REQUIRED ONLY FOR IN-PATIENT AND OUT-PATIENT SUBJECTS				
Biopsy				
Blood collection				
Chart review – prospective (FOR pre-SCREENING)				
Chart review – retrospective				
Review of existing data (ex: registry, Database , etc.)				
X-ray or Ionizing radiation exposure				
Clinical Tests				
Device implantation				
Drug administration				
EEG, EKG , ECG...etc				
Gene therapy, Genetic analysis				
Pregnancy/Breastfeeding Screening				
Interview, Questionnaire, Diary, Survey (please attach)				
Stool collection, Urine collection, or any Non-surgical Specimen collection				

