The subjects chemotherapy is decided by the Oncologist and/or Tumor Board in consultation. The duration of chemo similarly is also decided clinically. If the patient needs surgery or XRT

as part of the therapy, it is decided on entirely by the clinicians. The study is working around all of these clinical decisions.

Subjects will be called between visit 2 and 3 and then between visits 3 and 4. They will be asked if they had a side effects or event that may have been serious since the last study visit or telephone contact. They will also be asked if they were exposed to anyone who has chickenpox or shingles, and if they had any symptoms of shingles.

For 4 weeks after they receive their shot, they will be asked to record information about potential vaccine side effects on the vaccination Report Card.

14. Will the research involve the following?

N/A Chart/Data Review

Placebo Group No Yes (describe):

Other Control Group No Yes (describe): The control group is persons that do not get the vaccine.

Randomization No Yes (describe): We will obtain clinical information to determine eligibility this includes meds and PMH and then follow the subject's clinical course to know when to do the subsequent sampling. We will use a cloud based randomized tool to generate the list before the start for the whole study for what the order of vaccine or no vaccine will be. We will then have paperwork packets in the order of enrollment premade. We will open each packet at the consenting time and find vaccine or not and enroll and begin the study.

Deception No Yes (describe):

15. Does the research involve the use and/or disclosure of Individually Identifiable Health Information in any form or medium?

No Yes If yes, complete the required HIPAA Waiver/Authorization forms.

16. Does the study include the administration of a study agent that does not require FDA approval and does not require an IND (e.g. vitamins, food supplements, isotope tracers, alternative medicines, etc.)?

No Yes -provide a detailed description of the procedures used to assure patient safety:

17. Will radioactive material be administered or will subjects be exposed to ionizing radiation?

• Ex. Radiographic equipment, fluoroscopic equipment, and CT scanners, etc.

No Yes

18. In your judgment, could the objectives of the research be met in a way that presents less risk to subjects?

No Yes please explain:

Section 4 – Subject Selection, Recruitment, and Vulnerable Populations

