30 ZOSTAVAX

30 no vaccine

The Duke University site will have 15-ZOSTAVOX and 15 no vaccine

N/A SINGLE SITE

22. Duration of individual subject participation

Provide answers for each cohort including normal controls; (patients, family members, treating physicians,). 5 years or less depending on the duration of their chemo.

Chart/record review N/A

23. Age range of subjects

- provide answers for each cohort, including normal controls:

Adults 18 years or greater

Specific age range (list age range): 50 years and older for both cohorts

Children –waiver from VACO: attached pending- provide submission date:

**Contact AO/Research [contact] for guidance..

24. Which of the following will be recruited or reviewed for this study (check all that apply)?

Veteran Inpatients

Men

Veteran Outpatients

Women

Veteran Families

*Normal volunteers

*Non-Veterans; Provide justification

*According to VHA Handbook 1605.04 Notice of Privacy Practices VHA must provide a copy of its VHA Notice of Privacy Practices to all non-Veteran patients (e.g., active duty personnel or those seeking care in humanitarian circumstances) receiving care or treatment at a VHA health care facility or non-Veteran research subjects enrolled in an approved VHA research study with clinical trials. VA Form 10-0483 Acknowledgement of the Notice of Privacy Practices should be signed by the non-Veteran research subject at the time of consent and given a copy of the Notice of Privacy Practices. Once the Acknowledgement Form is signed please send a copy to the Privacy Officer. If additional information is needed please contact your Facility Privacy Officers [name] or [name] [contact] / [contact] [contact] / [contact].

25. Which vulnerable population(s) will be TARGETED for recruitment in this study:

- Indicate only those populations that are specifically targeted for the research described in this document.
- *It is not necessary to check any box if, for example, your study will include a full range of subjects, some of whom may be elderly or subjects who might incidentally be employees.*

- N/A Chart Review (proceed to Item 30)
- NONE (proceed to Item 26)
- Medical students, house staff, or Employees of the VAMC or Case
- Pregnant Women OR Women who are Breastfeeding, Human Fetuses, or Neonates
- Children – Complete Section 14 “Children as Research Subjects”
- Prisoners (The LSCDVAMC does not conduct research involving prisoners)
- Targeting Persons over Age 65

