Safety and tolerability will be assessed by statistical and clinical review of all safety data collected throughout the study. All subjects who are vaccinated and provide any safety follow-up will be included in safety analyses and summaries. To provide an overall assessment, the incidence rate for the vaccination group and no-vaccination group, the risk difference between the two groups and the associated 95% CI will be provided for broader safety measures such as the proportions of the subjects with any: adverse experiences; injection-site adverse experiences; systemic adverse experiences; serious adverse experiences; or vaccine-related serious adverse experiences after vaccination.

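### The SAP's safety set admits only vaccinated subjects although a risk difference against unvaccinated controls is promised, and equivalent early event collection in controls is not described

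*SAP*

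**What the plan says.** The safety paragraph of SAP section 2.7 sets the analysis population in one sentence: "All subjects who are vaccinated and provide any safety follow-up will be included in safety analyses and summaries". The sentence after it commits to reporting "the incidence rate for the vaccination group and no-vaccination group, the risk difference between the two groups", with a 95% CI, for any adverse experience, injection-site, systemic, serious, and vaccine-related serious experiences. The material reviewed is "all safety data collected throughout the study".

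Protocol item 13 describes two routes of event collection. The first is the report card: "For 4 weeks after they receive their shot, they will be asked to record information about potential vaccine side effects". The second is telephone contact: "Subjects will be called between visit 2 and 3 and then between visits 3 and 4". The calls are not restricted by arm, and each asks about the period since the previous visit or call. Item 29, on materials handed to subjects, says that enrollees will complete the card and does not mention arm. Item 14 makes the control group people who receive no vaccine, without placebo. Item 22 puts individual participation at "5 years or less depending on the duration of their chemo".

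**The concern.** Safety is a named hypothesis (item 9, Hypothesis 5: "We hypothesize that ZOSTAVAX is safe if given to subjects with solid organs tumors"). The section 2.7 risk differences are the only between-arm safety summaries in the supplied text. Two things undermine them.

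First, the population rule and the analysis it feeds disagree. Controls have no inclusion rule, no stated start date and no stated window, so two analysts following the text could use different denominators and periods.

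Second, if the card goes only to vaccinated subjects, minor events soon after day 0 are recorded prospectively in one arm and not in the other. The any-event and systemic-event differences would then lean toward apparent harm from the vaccine even if true risks were equal. The monthly toxicity review in item 63 covers the study as well as the cards, so only its card part would lack a control comparator.

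**Working it through.** The plan states no safety rate or safety precision, so there is no figure of its own to reproduce.

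**1. Population rule against analysis.** Planned enrolment per arm is 30 (Cleveland) + 15 (Duke) = 45 (protocol items 20 and 21).

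- Rule as written: up to 45 vaccinated subjects and 0 controls. The risk difference x₁/45 − x₀/0 is undefined.
- Both arms admitted: 45 against 45. The Wald 95% half-width is 1.96 × √(2p(1−p)/45). At assumed event rates of 5%, 10%, 20%, 30% and 50% in both arms it is 9.0, 12.4, 16.5, 18.9 and 20.7 points.

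**2. Interval without described control collection.** Visits are taken to be the blood draws. Item 13 puts the second draw at least 14 days after vaccination, and later when surgery intervenes. Controls are assumed to keep the same timing. The first call falls after visit 2 and asks back to the last contact, so on item 13's wording it does not reach the visit 1 to visit 2 interval. The share of the 28 card days before visit 2 is min(gap, 28)/28; a 14-day gap gives 14/28 = 50%. This is a share of the card window only, not of a study-long measure.

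**3. Illustration of the bias if the card is one-arm.** Only the 45 per arm comes from the documents. Assumed:

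- p: true early event risk, equal in both arms, 30% to 50%
- c: fraction of control early events captured (all captured in the vaccine arm)
- q: share of subjects with a later captured event, independent of the early one

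Vaccine arm: 1 − (1−p)(1−q). Control arm: 1 − (1−cp)(1−q). Spurious difference: p(1−c)(1−q).

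Example: p = 0.5, c = 0.5, q = 0.7 gives 0.5 × 0.5 × 0.3 = 7.5 points. With equal capture each arm would show 1 − 0.5 × 0.3 = 0.85, and the half-width is 1.96 × √(2 × 0.85 × 0.15/45) = 14.8 points.

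Results in percentage points; ranges run over p = 30% to 50%:

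| q | c = 90% | c = 75% | c = 50% | Half-width, equal capture |
|---|---|---|---|---|
| 0 (28-day window) | 3–5 | 7.5–12.5 | 15–25 | 18.9–20.7 |
| 50% | 1.5–2.5 | 3.8–6.3 | 7.5–12.5 | 17.9–19.7 |
| 70% | 0.9–1.5 | 2.3–3.8 | 4.5–7.5 | 14.8–16.8 |
| 90% | 0.3–0.5 | 0.8–1.3 | 1.5–2.5 | 9.0–10.5 |

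The q = 0 row needs a 28-day endpoint, which the plan does not specify. The other rows correspond to a measure run over the whole study.

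**The case against.** The intent to include controls is plain from the sentence that promises their incidence, so a reader who infers that the plan drops controls from safety goes too far. That stands. But intent supplies no denominator rule, start date or window. The closing reference to the time after vaccination may qualify only the last listed measure, so it does not by itself show that every measure is anchored to the injection.

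On collection, a reader might infer that items 13 and 29 flatly contradict each other. The better reading is that item 29 is loose shorthand: it separates those who enrol from those who do not, and is silent on arm. That leaves an ambiguity. If item 29 means every enrollee, most of the inequality disappears; if item 13 governs, it remains.

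Nor do the documents support the inference that controls have no safety follow-up. The calls cover both arms. Anchoring recall to the last visit suggests that events may be asked about at visits, although the supplied text does not say so. Item 12 ticks chart review and a questionnaire or diary as research procedures, and item 14 has staff following the clinical course (to time sampling), all without restriction by arm. None of this establishes adverse-event collection, but it bears on serious events in particular. The card, the schedule figure and the consent form are not available here, and any of them might settle who completes the card.

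Finally, this is a pilot with descriptive safety and no decision rule for harm, so the damage is to the interpretation of an estimate.

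**Conclusion.** The population rule contradicts the analysis that it feeds and should be corrected; this rests on the SAP wording alone. The collection point holds in a limited form: as item 13 is written, no equivalent early event collection is described for controls over at least 14 days (same visit timing assumed), and item 29 does not resolve it.

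If the card is one-arm, the direction of bias is toward apparent vaccine harm, mainly through non-serious events before visit 2. Its size cannot be computed from the documents. It is tempting to cite 15 to 25 points, but that needs 50% capture in controls and a 28-day endpoint that the plan does not define. For a whole-study any-event measure the bias is probably small relative to the interval, unless capture is poor and later events are few. Confidence is medium, because the material that would show who completes the card was not supplied.

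**What to change.** (a) In SAP section 2.7, define the safety set as all randomised subjects with any safety follow-up, analysed by vaccine received. Take day 0 (visit 1) as the common start, and use the same observation window in both arms for the any-event, systemic and serious risk differences.

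(b) Reconcile protocol items 13 and 29 so that events from day 0 to visit 2 are collected the same way in both arms. One way is the same four-week card, without injection-site items for controls, and the same adverse-event question to everyone at visit 2. If the card stays with the vaccinated arm, limit the risk differences to events collected alike in both arms, and report card-only events for the vaccinated arm alone.

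Reporting a 28-day window ahead of the whole-study figure is optional. The argument for it is sensitivity: with 70% of subjects having a later event, a real 15-point early excess would show as 15 × (1 − 0.7) = 4.5 points over the whole study.

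The cost is a few sentences of SAP and protocol text and, if the shared card is adopted, a small burden on about 45 controls and one question at an existing visit. Without a placebo, open-label differences in reporting remain, and the SAP should say so.

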Surgical procedure or Specimen removal during surgery				
Tissue banking (complete Section 12)				
Use of pre-existing tissues/specimens				
Other (list):				

- **Standard of care procedures are procedures performed in the course of normal medical care.*
- ***Research Procedures are performed for the purposes of this research alone.*

13. Please describe the research design and all study related procedures.

- Describe ALL PROCEDURES ASSOCIATED WITH THIS RESEARCH. This includes standard of care and research procedures.
- For complex studies please include diagrams and tables. Be sure to describe when each procedure will be performed. Be sure to provide information for each cohort, including normal controls.

Study participants based on the inclusion and exclusion criteria listed below will be recruited from the Oncology clinics and medical services of the Cleveland VA. The study oncologist will review the study with them. Subjects that consent will be randomized to one of the two arms, vaccine or no vaccine. Individuals will undergo blood draws for immunologic assays according to time points depicted in the figure below. Each blood draw (25 ml each) has been timed to follow routine clinical monitoring as ordered by the oncologist for maximum feasibility.

- The first blood draw will be at the time of consent into the study. We anticipate this time to be the first visit with the oncologist. They will receive ZOSTAVAX on that day if they are in that arm of the study.
- The second blood draw will be on the day of chemotherapy initiation, no earlier than 14 days post-vaccination. This will be longer than 14 days for example when there is surgery between the vaccination and the start of chemotherapy.
- The third blood draw will be at the start of the second chemotherapy cycle.
- The fourth blood draw will be 3-24 months post chemotherapy cessation. The timing of the final blood draw is based on cessation of chemotherapy and not any concurrent radiation therapy that would be also completed by the 3-6 month post-chemotherapy sampling.

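### The safety comparison has no early analysis window and no split at chemotherapy start, so background events can mask an early vaccine effect on any, systemic and serious adverse experiences; the safety set and start point are also undefined for controls

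*SAP*

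**What the plan says.** The safety paragraph of SAP 2.7 opens: "Safety and tolerability will be assessed by statistical and clinical review of all safety data collected throughout the study". It defines the analysis set in one sentence: "All subjects who are vaccinated and provide any safety follow-up will be included in safety analyses and summaries". It then states that "the incidence rate for the vaccination group and no-vaccination group, the risk difference between the two groups and the associated 95% CI will be provided". The measures are the proportions of subjects with any adverse experience, any injection-site one, any systemic one, any serious one, and finally "vaccine-related serious adverse experiences after vaccination". No period of counting is given.

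Protocol item 13 sets the timeline. Consent, the first draw and, in that arm, vaccination fall on one day. Then: "The second blood draw will be on the day of chemotherapy initiation, no earlier than 14 days post-vaccination". The gap is longer when surgery comes first. The fourth draw is 3-24 months after chemotherapy stops, and item 22 allows participation of up to 5 years.

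Safety information comes from two sources in item 13. One is a report card kept for 4 weeks after the shot. The other is two telephone calls, one between visits 2 and 3 and one between visits 3 and 4. Item 29 says that those who enrol complete the card, without limiting it to vaccinees.

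Hypothesis 5 (Protocol item 9) reads in part: "We hypothesize that ZOSTAVAX is safe if given to subjects with solid organs tumors at least 14 days prior to initiation of chemotherapy". No safety margin is attached to it.

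**The concern.** The proportion of subjects with at least one event saturates as follow-up lengthens. Once most subjects in both arms have had an event during chemotherapy, or around surgery, a subject who also reacted to the vaccine adds nothing to the count. The whole-study difference is a legitimate description of cumulative experience. It answers poorly the question in Hypothesis 5, which is whether the vaccine itself causes harm when given shortly before chemotherapy. A small whole-study difference could be taken as support for that hypothesis when the measure had little capacity to show otherwise. The pilot is meant to inform a larger study, so the weakness could carry forward.

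The second gap is one of definition. The stated safety set contains vaccinees only, yet the paragraph compares them with a no-vaccination group. The only start point named is vaccination, which controls do not have.

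**Working it through.** **Is there a figure to reproduce?** No. The documents give no adverse-event rate, safety margin, interval width or power for safety. The rates below are assumptions.

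**Inputs from the documents.** Planned arm size is 30 + 15 = 45 (Protocol items 20 and 21; 90 in total in SAP 2.7). Earliest chemotherapy start is day 14. Last draw is 3-24 months after chemotherapy (item 13).

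**Assumptions.** Proportion with an event before chemotherapy: 30% (vaccine) and 10% (control). Proportion b with an event from chemotherapy start onward, equal in both arms and independent of early events: 50%, 80%, 90% or 95%. Events are captured equally in both arms.

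**Formula.** Whole-study proportion = 1 - (1 - p)(1 - b), so the risk difference is (0.30 - 0.10)(1 - b). In general, with vaccine-caused risk v and total background risk q, the risk difference is v(1 - q). Here v = 0.20/0.90 = 0.222 and 1 - q = 0.90(1 - b), which gives the same 0.20(1 - b).

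The Wald 95% half-width is 1.96 × √{[p₁(1 - p₁) + p₀(1 - p₀)]/45}.

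| Counting period | Vaccine | Control | Difference (points) | Half-width (points) |
|---|---|---|---|---|
| Before chemotherapy | 30% | 10% | 20 | 16.0 |
| Whole study, b = 50% | 65% | 55% | 10 | 20.1 |
| Whole study, b = 80% | 86% | 82% | 4 | 15.1 |
| Whole study, b = 90% | 93% | 91% | 2 | 11.2 |
| Whole study, b = 95% | 96.5% | 95.5% | 1 | 8.1 |

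For example, at b = 80%: 1 - 0.70 × 0.20 = 0.86 and 1 - 0.90 × 0.20 = 0.82. The half-width is 1.96 × √[(0.1204 + 0.1476)/45] = 0.151.

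**Other effect sizes.** Moving from q = 0.10 to q = 0.90 takes the difference from 0.090 to 0.010 at v = 0.10, from 0.180 to 0.020 at v = 0.20, and from 0.315 to 0.035 at v = 0.35.

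**Which measures are affected.** The formula applies to any, systemic and serious events. The loss is smaller wherever background is lower. For injection-site events q is about 0, because controls have no injection, so the difference equals v in any window. Vaccine-related serious events are filtered by attribution and are not materially diluted.

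**A bias in the other direction.** Both calls come after visit 2, the day of chemotherapy initiation. If only vaccinees keep the card, early events in controls are collected less actively. Suppose controls report a share s of early events and the vaccine has no effect. The early difference is then q(1 - s): with q = 0.20 and s = 0.5 it is 0.20 × 0.5 = 0.10, a spurious 10 points. An early window therefore needs equal collection in both arms to be interpretable.

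**The case against.** The strongest reply is that safety does not rest on these risk differences alone. SAP 2.7 also plans clinical review of all the data and offers the listed measures as examples for an overall assessment. Protocol item 63 has the team review report cards at least monthly. This stands: early reactions would not go unseen, and it would be wrong to say that the plan has no other look at Hypothesis 5. These reviews are not, however, between-arm comparisons.

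A reader might infer four stronger things that the documents do not support.

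- **Chemotherapy toxicity hides all five measures.** Injection-site events are listed separately and are untouched; vaccine-related serious events are essentially so.
- **Controls have no possible start date.** Randomisation packets are opened at consent (item 14), the first draw and vaccination share that day (item 13), and SAP 2.7 already uses day 0 for fold change in both groups. The gap is one of drafting. The reference to vaccination may also attach only to the last measure, in which case the other four have no stated start.
- **The whole-study result would be a narrow interval around zero that shows safety.** At 80% background the half-width is 15 points against 16 before chemotherapy, so the interval runs from about -11 to +19. It narrows clearly only at higher backgrounds.
- **The error runs only toward zero.** Unequal early collection can push the difference away from zero.

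It is also fair to say that the 4-week card is a time window. It is a collection window, and the SAP does not use it for analysis. Its days 14-28 can already overlap chemotherapy. Finally, two telephone calls may not capture all chemotherapy toxicity, and lower capture would mean less dilution.

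**Conclusion.** The concern holds for three of the five measures. Without an early analysis window or a split at chemotherapy start, the planned risk differences for any, systemic and serious events lose sensitivity to an early vaccine effect by the factor (1 - b). Under the assumed 30% and 10% early rates, 20 points become 10, 4 or 2 at 50%, 80% or 90% later background. The direction follows from the counting rule. The size rests on assumed rates, independence of early and later events, and equal capture, none of which the documents settle. The safety set and the start of counting also need definition for the no-vaccine arm. This is a cheap improvement to a descriptive pilot analysis, held with moderate confidence.

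**What to change.** In SAP 2.7:

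1. Define the safety set as all randomised subjects with any safety follow-up.
2. Count events from day 0 (the consent and randomisation visit) in both arms.
3. Report proportions and risk differences separately for day 0-28, for day 0 to the day before chemotherapy initiation, and for chemotherapy initiation to the final draw, beside the whole-study totals. State that the pre-chemotherapy window varies in length between subjects and may include surgery.
4. Summarise injection-site and vaccine-related serious events in vaccinees, with exact confidence intervals.

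In the Protocol, reconcile items 13 and 29 so that controls also complete the 4-week card. If that is not done, label the early comparison as subject to unequal ascertainment.

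The cost is SAP wording, use of event onset dates, a few extra table columns and a card for controls. The early windows will hold fewer events, so their intervals will be wide relative to the rates they estimate.

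### The between-arm risk difference planned for injection-site and vaccine-related serious events compares against a control rate that is zero by design, and its interval can be misread when counts are low

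*SAP*

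**What the plan says.** The safety paragraph of SAP 2.7 states that "the incidence rate for the vaccination group and no-vaccination group, the risk difference between the two groups and the associated 95% CI will be provided". The measures named are any adverse experience and then "injection-site adverse experiences; systemic adverse experiences; serious adverse experiences; or vaccine-related serious adverse experiences after vaccination". All five get the same treatment. None is marked as applying to the vaccine arm only, and no interval method is named beyond "the associated 95% CI".

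Protocol item 14 describes the comparator in one line: "The control group is persons that do not get the vaccine". Item 13 gives the two arms as vaccine and no vaccine. Neither document describes a placebo or sham injection.

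**The concern.** A control subject has no study injection site, and a serious event in a control cannot be attributed to a vaccine that was not given. For these two measures the control proportion is therefore fixed at zero by the design, not estimated from data. Subtracting it gives back the vaccine-arm incidence. What changes is the interval, which is built as if two unknown proportions were being compared.

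This matters most for vaccine-related serious events. Hypothesis 5 (Protocol item 9) is that the vaccine is safe when given before chemotherapy, and item 44 notes that it is a live attenuated vaccine. These events bear closely on that hypothesis, and counts are likely to be small. A table reader could take an interval that covers zero as showing no excess, or a 0-to-0 interval as certainty, when neither follows.

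**Working it through.** **Inputs.** Arm size: 30 at Cleveland plus 15 at Duke in each arm (Protocol items 20 and 21), so 45 per arm; this matches the SAP total of 90. As a sensitivity check, 38 per arm, from the 76 subjects for full analysis in SAP 2.7. The 95% level is taken as two-sided (z = 1.96). Event counts are assumed and shown as a range, because neither document gives an expected rate. The SAP states no safety rate, interval width or power, so there is no planned figure to reproduce.

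**Formulas**, for x events among n vaccinated and 0 among n controls, with p = x/n:

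- Wald difference: p ± z·√[p(1−p)/n + 0·(1−0)/n]. The control term is zero, so this equals the vaccine arm's own Wald interval.
- Newcombe difference: lower = p − √[(p − l₁)² + u₂²], upper = p + √[(u₁ − p)² + l₂²]. Here (l₁, u₁) and (l₂, u₂) are the Wilson limits for the vaccine arm and for 0/n. At n = 45, l₂ = 0 and u₂ = 3.84/(45 + 3.84) = 7.9%.
- Exact vaccine-arm interval: Clopper-Pearson. With x = 0 the upper limit is 1 − 0.025^(1/45) = 7.9%.

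**Worked case, x = 2, n = 45.** p = 4.4%. Wald half-width = 1.96 × √(0.0444 × 0.9556/45) = 6.0 points, giving -1.6 to 10.5. The Wilson limits are 1.2 and 14.8, so the Newcombe lower limit is 4.4 − √(3.2² + 7.9²) = -4.1 and the upper limit is 14.8. Exact: 0.5 to 15.1.

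**Results at 45 per arm** (percentage points):

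| Events | Estimate | Wald difference | Newcombe difference | Exact, vaccine arm |
|---|---|---|---|---|
| 0 | 0.0 | 0.0 to 0.0 | -7.9 to 7.9 | 0.0 to 7.9 |
| 1 | 2.2 | -2.1 to 6.5 | -5.9 to 11.6 | 0.1 to 11.8 |
| 2 | 4.4 | -1.6 to 10.5 | -4.1 to 14.8 | 0.5 to 15.1 |
| 3 | 6.7 | -0.6 to 14.0 | -2.3 to 17.9 | 1.4 to 18.3 |
| 4 | 8.9 | 0.6 to 17.2 | -0.6 to 20.7 | 2.5 to 21.2 |
| 5 | 11.1 | 1.9 to 20.3 | 1.1 to 23.5 | 3.7 to 24.1 |
| 9 | 20.0 | 8.3 to 31.7 | 8.0 to 33.8 | 9.6 to 34.6 |
| 15 | 33.3 | 19.6 to 47.1 | 19.0 to 47.9 | 20.0 to 49.0 |
| 22 | 48.9 | 34.3 to 63.5 | 32.9 to 63.0 | 33.7 to 64.2 |

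The difference interval goes below zero for 1 to 3 events under Wald and for 0 to 4 under Newcombe. The true difference cannot be negative, because the control rate is zero. From 5 events upward both intervals lie above zero. From 9 upward every limit is within about 3 points of the exact one.

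**At 38 per arm** the crossing counts are the same. With no events the exact upper limit is 9.3% and Newcombe gives -9.2 to 9.2.

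**Two separate mechanisms.** Under Newcombe, the negative limits come from giving the structural zero its own uncertainty (u₂ = 7.9%). Under Wald, the control adds nothing; the 0-to-0 interval and the negative limits are ordinary failures of Wald with sparse data. The SAP names neither method, so which failure would appear is unknown.

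**The case against.** The best defence is that nothing is lost. The same SAP sentence plans the incidence in each arm, so two vaccine-related serious events would appear as 2/45 beside 0/45. Subtracting a true zero does not shrink the estimate. The paragraph also plans clinical review of all safety data, and Protocol item 63 plans at least monthly review of the report cards. The comparison is descriptive, in a pilot, and no test, margin or decision rule turns an interval covering zero into a finding of safety.

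Most of that stands, and it rules out two stronger readings that a reader might infer. The first is that these intervals are wrong in general. They are not: from about 5 events upward they lead to the same conclusion as the exact interval. The second is that the plan could hide real vaccine reactions. The documents do not support that, because counts and incidences are reported by arm whatever the interval shows.

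What the defence does not answer is why the contrast should be shown at all for these two measures. It tells the reader nothing that the vaccine-arm incidence does not, and at the counts plausible for rare serious events its error bars are the poorer summary.

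It is also fair to say that larger questions sit in the same paragraph. The safety set is described as "All subjects who are vaccinated and provide any safety follow-up will be included in safety analyses and summaries", which leaves the control denominator and start date undefined. Those questions affect the measures where comparison is meaningful. They are separate from this one, and settling them would not settle it.

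**Conclusion.** The point holds in limited form. For injection-site and vaccine-related serious adverse experiences, SAP 2.7 specifies a contrast with a structural zero that carries no comparative information. At about 0 to 4 events of 45, its interval can be misread. The clearest case is zero events: the data would still be compatible with a rate of up to 7.9% (9.3% at 38 vaccinated), while the planned interval would show either 0 to 0 or a symmetric range of which half is impossible.

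This rests on four assumptions: 45 (or 38) vaccinated subjects with safety data; a two-sided 95% interval by Wald or Newcombe; low event counts, since no rates are given; and no control vaccinated during safety follow-up. Severity is minor. It is a free improvement to reporting and does not affect the conduct of the trial or its primary analysis.

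**What to change.** In the safety paragraph of SAP 2.7:

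1. Report injection-site and vaccine-related serious adverse experiences for the vaccine arm only, as x/n with an exact (Clopper-Pearson) 95% CI and no between-arm difference. Show the control column as not applicable.
2. Keep the risk difference for any, systemic and all-cause serious adverse experiences, where controls can have events.
3. Name the interval method for those differences and choose one valid with zero cells, for example Newcombe or Miettinen-Nurminen. Confirm that the software returns limits when a cell is zero.

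The cost is a few lines of SAP wording and two table rows. Data collection, sample size and visits do not change.
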